Subject Information – charts, records, images, or specimens are considered ‘subjects’

Target accrual is the proposed number of subjects to be included in your study at your site. “Subjects” may include Mayo Clinic charts, records, or specimens, and/or charts, records, or specimens received at Mayo Clinic from external sources for collaborating analysis by the investigator under this IRB application:

Target accrual: 100

Subject population: patients with confirmed or suspected Crohn’s disease.

Inclusion criteria: Crohn’s disease patients with involvement of terminal ileum (thickness > 3mm) or other segments of small or large bowel, age above 18.,

Exclusion criteria: patients with change of medicine or going to surgery over the 6-months follow-up period, patients with unreliable ultrasound images due to conditions such as large body habitus or poor ultrasound imaging window; adults lacking capacity to consent; vulnerable subjects such as prisoners. Pregnant women, nursing mothers, patients with known or suspected right-to-left, bi-directional, or transient right-to-left cardiac shunts, patients with history of hypersensitivity allergic reactions to ultrasound contrast agents.

Yes No Will a Certificate of Confidentiality (COC) be obtained from NIH? If yes,

Who is obtaining the COC: Mayo Clinic investigator, study sponsor, other:

Explain why a COC is needed:

Study Design

Methods: *Describe, in detail, the research activities that will be conducted under this protocol:*

Study Design: We will study the terminal ileum of 100 Crohn’s disease patients to investigate the efficacy of ultrasound measurements for disease evaluation and treatment outcome prediction. Patients with ongoing medical therapy or starting a new medical therapy will be recruited. Inflammation and fibrosis evaluated by contrast enhanced MR enterography at baseline and 6-months post therapy will be used as the reference standard. Ultrasound will be performed at baseline, 4-weeks, and 6-months. For Aim 1, correlation of ultrasound measurements with MR enterography results will be evaluated at baseline and 6-months. For Aim 2, we will assess the association of the percentage change in ultrasound parameters from baseline to 4-weeks with the percentage change in MR enterography scores from baseline to 6-months. More information about data analysis can be found in the statistical section below.

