Street address, city, county, precinct, zip code, and their equivalent geocodes		
Phone or fax numbers		
Account, member, certificate or professional license numbers, health beneficiary numbers		
Vehicle identifiers and serial numbers, including license plate numbers		
If None of the above identifiers will be recorded or maintained in the dataset and/or sent outside of the study team, please check "None".	 None	 None

Statistical Information

Note: Power analyses and study endpoints are not needed for a pilot or feasibility studies.

No statistical information. *If checked, please explain:*

Statistical Considerations

Power Statement:

The sample-size for the present investigation was determined for the primary aim of assessing the correlation between ultrasound parameters and the MaRIA score (a score calculated from MR enterography, which reflects bowel inflammation [1]). For ultrasound to have meaningful clinical utility we would require a correlation with MaRIA score of at least 0.70. For the primary analysis, the correlation between ultrasound measurements and MaRIA score will be compared to 0.70 using a two-tailed, alpha=0.05 level test. Under the assumption that the “true” correlation is 0.82, a sample-size of N=100 will provide statistical power of 82% for the primary analysis.

Data Analysis Plan:

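### The 82% power holds for about 100 analysable ultrasound–MaRIA pairs, but accrual is also 100 and some exclusions act after enrolment, with no loss allowance or replacement rule

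*Combined protocol and SAP*

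**What the plan says.** The Power Statement (Statistical Considerations) sizes the study for the correlation between ultrasound parameters and the MaRIA score. The threshold is set by "we would require a correlation with MaRIA score of at least 0.70", and the comparison with 0.70 is made "using a two-tailed, alpha=0.05 level test". Assuming a true value of 0.82, the statement concludes that "a sample-size of N=100 will provide statistical power of 82% for the primary analysis".

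Under Subject Information the accrual line reads "Target accrual: 100". The form explains this number as follows: "Target accrual is the proposed number of subjects to be included in your study at your site". The Methods paragraph repeats it: "We will study the terminal ileum of 100" Crohn's disease patients.

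The exclusion criteria in the same section cover "patients with change of medicine or going to surgery over the 6-months follow-up period, patients with unreliable ultrasound images". They are written for the study as a whole and are not tied to a particular analysis.

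The Methods paragraph places the Aim 1 correlation at both baseline and 6 months. Neither it nor the Data Analysis Plan says which is primary. The documents contain no dropout allowance, replacement rule, missing-data rule or definition of an evaluable set.

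**The concern.** The same number, 100, serves as the accrual target and as the analysed sample in the power calculation. Two exclusions cannot be fully applied at enrolment: image quality is known at the scan, and a change of medicine or surgery is known only as the 6 months pass. If 100 patients are accrued and any of them is then excluded and not replaced, fewer than 100 pairs reach the primary test.

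Such losses are foreseeable from the protocol. Its Background says that follow-up imaging guides changes in therapy, that fibrostenotic disease usually leads to surgery, and that ultrasound may not reach deep bowel loops.

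Two things are at stake:

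- **Power.** A true correlation of 0.82 would fail to be distinguished from 0.70 more often than the sponsor expects.
- **Selection.** A baseline ultrasound and a baseline MR enterography form a complete pair on the day they are taken. Removing that pair because of what happens months later wastes information. It also makes the baseline sample depend on clinical course, since it takes out the patients who go to surgery, a group that the Background links to fibrosis.

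**Working it through.** **Inputs.** From the Power Statement: null correlation 0.70, assumed true correlation 0.82, two-sided alpha 0.05, N = 100, stated power 82%. From Subject Information: target accrual 100. The documents give no loss rate, so 5% to 30% is used as an assumed range.

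**Formula.** For a one-sample test of a correlation on the Fisher z scale,

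power = Φ( (atanh 0.82 − atanh 0.70) × √(n − 3) − 1.960 ).

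Here atanh 0.82 = 1.1568 and atanh 0.70 = 0.8673, so the difference is 0.2895.

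**Reproducing the stated figure.** At n = 100, 0.2895 × √97 = 2.851, and 2.851 − 1.960 = 0.891. Φ(0.891) = 0.814, or 81.4%. A bias-corrected Fisher z gives 81.5%, and simulation of bivariate normal data (100,000 replicates) gives 82.5%. The stated 82% is confirmed. A one-sided test at 0.05 would give 88.6%, so the two-sided reading is the one that was used.

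**Power if accrual stays at 100 and losses are not replaced.**

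| Assumed loss | Pairs | Power, Fisher z | Power, simulation |
|---|---|---|---|
| 0% | 100 | 81.4% | 82.5% |
| 5% | 95 | 79.3% | 80.5% |
| 10% | 90 | 77% | 78.7% |
| 15% | 85 | 74.6% | 76.3% |
| 20% | 80 | 71.9% | 73.8% |
| 30% | 70 | 65.9% | 68.1% |

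For example, at n = 80: 0.2895 × √77 = 2.540, 2.540 − 1.960 = 0.581, and Φ(0.581) = 0.719. The chance of missing a true 0.82 then rises from 18.6% to 28.1%.

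**How much loss can be absorbed.** Solving for 80% power: n = ((1.960 + 0.842) / 0.2895)² + 3 = 96.6, so 97 pairs. At 97 pairs power is 80.2%, and at 96 it is 79.7%. By Fisher z, up to 3 lost pairs keep power at 80%. Simulation is slightly more lenient (80.5% at 95 pairs).

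**Accrual that would preserve 100 pairs,** 100 / (1 − loss), rounded up: 106 at 5%, 112 at 10%, 118 at 15%, 125 at 20%, 143 at 30%.

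**Selection.** The documents do not allow the effect of dropping baseline pairs on the correlation itself to be calculated, in size or direction. This part rests on the wording: the exclusion is study-wide, and nothing in the Methods or the Data Analysis Plan keeps the baseline pair of a patient who is excluded later.

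**The case against.** The strongest reply is that 100 may already be the number left after exclusions. The form speaks of subjects to be included, and a patient who meets an exclusion criterion can be regarded as not included. On that reading excluded patients are replaced and the power statement stands. Unreadable images could likewise be handled as screening failures at the first scan. The medicine and surgery criterion might mean changes already planned at screening. If the primary correlation is at baseline and patients excluded later keep their baseline pair, follow-up events cost it no power.

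These readings are possible, and they limit what can be claimed. A reader might infer three stronger things that the documents do not support:

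- **That the power figure is miscalculated.** It is not; it reproduces.
- **That accrual is capped at 100, so the design cannot deliver 82%.** The text gives a target, not a cap, and does not forbid replacement. Any shortfall depends on a loss rate that is nowhere documented, and it is small if few pairs are lost.
- **That the plan expressly discards baseline pairs.** No analysis section says so. This follows only from reading a study-wide exclusion as it is written.

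What survives is that the documents state none of the favourable readings. They contain no replacement rule, no definition of evaluable patients, no named primary time point and no provision to keep baseline data. One criterion, read plainly, refers to the follow-up period.

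**Conclusion.** The point holds in a conditional form. The 82% is right for about 100 analysable pairs and has almost no margin below that. If 100 means patients accrued and exclusions are not replaced, power is about 79%, 77%, 72% or 66% at 5%, 10%, 20% or 30% loss. These rates are assumptions, and the figures rest on the Fisher z approximation; simulation runs about 1 to 2 points higher. With no more than 3 lost pairs, or with replacement, there is no material shortfall.

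Separately, the follow-up exclusion as worded would remove complete baseline pairs from the Aim 1 correlation because of later events. That loss is avoidable, and it selects the baseline sample on clinical course. Its effect on the estimate cannot be sized from the documents.

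**What to change.** 1. **Power Statement.** Say that 82% power refers to 100 evaluable pairs. Add that if 5%, 10%, 20% or 30% of the accrued patients are not evaluable, power is about 79%, 77%, 72% or 66%. If 100 is instead meant as the number remaining after exclusions, say so and add the replacement rule.
2. **Data Analysis Plan and exclusion criteria.** Name baseline as the time point of the primary correlation. Keep in it every patient with a readable baseline ultrasound and a baseline MR enterography. Apply the medicine-change and surgery exclusion only to the 6-month and Aim 2 analyses.

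The second change removes follow-up events as a source of loss for the primary test. It does not help with unreadable images, so the first is still needed.

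The cost is a few sentences and no extra patients. The stated power becomes less favourable, and the baseline and 6-month analyses will rest on different patient sets, which the report should make plain. If the sponsor would rather protect 100 evaluable pairs, accrual can be raised by 100 / (1 − loss) with a justified loss rate, for example 112 at 10% or 125 at 20%. That option does need more patients.

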Ultrasound Evaluation of Crohn's Disease

NCT03235180

September 28, 2017

IRB Minimal Risk Protocol Template

General Study Information

Principal Investigator: [name], [name], [name]

Study Title: Ultrasound Evaluation of Crohn's Disease

Protocol version number and date: 9/28/17

Purpose

Hypothesis: Small bowel stiffness and vascularity measured by ultrasound imaging are useful biomarkers for Crohn's disease.

Aims, purpose, or objectives:

The overall goal is to investigate the value of ultrasound measurements of small bowel stiffness and vascularity as new biomarkers for Crohn's disease.

Background (*Include relevant experience, gaps in current knowledge, preliminary data, etc.*):

Crohn's Disease (CD) is a chronic inflammatory condition in the bowel that affects over 1 million Americans, costing billions of dollars every year. Due to the relapsing nature of the disease, frequent imaging follow-ups are often necessary over many years to monitor treatment response to guide therapy adjustments. An ideal CD imaging method should be able to evaluate both inflammation and fibrosis, as patients with predominantly inflammatory lesions are more likely to respond to medical therapy, while patients with fibrostenotic lesions usually require surgery. Ultrasound is safe, cost-effective, and widely accessible, thus provides an attractive alternative to the clinical standard Computed Tomography (CT, risks of radiation) and Magnetic Resonance Imaging (MRI, more expensive and limited accessibility). Because ultrasound may not be able to image bowel loops deep in the body, its main role is to follow-up after initial screening by CT or MRI (especially for terminal ileum, which is easily accessible by ultrasound and the most frequently affected bowel segment for CD).

In this project, we will study the efficacy of ultrasound shear wave elastography and vascularity imaging for CD evaluation. Literature evidences demonstrate that bowel stiffness is correlated with fibrosis, while bowel vascularity and perfusion is correlated with inflammation. Therefore, we expect the combination of shear wave elastography and vascularity imaging can increase the sensitivity and specificity of CD evaluation.

Aim 1: To evaluate the correlation of ultrasound measurements with clinically indicated Magnetic Resonance Enterography (MRE).

Aim 2: To investigate if ultrasound measurements can be used to predict treatment response for Crohn's disease.

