Ultrasound Procedure: Patients will be fasting for 4 hours before ultrasound scans to reduce bowel air and peristalsis. The ultrasound transducer will be sanitized as per clinical routine before each use. The terminal ileum (TI) will be located by B-mode ultrasound. The TI lesion with the most significant thickening will be

identified in B-mode images for subsequent measurements. Repeated measurements of shear wave speed (which represents bowel stiffness) at the TI lesion will be obtained using the GE Logiq E9 ultrasound scanner. Vascularity images of the TI lesion will be obtained using the Verasonics ultrasound scanner. We will obtain ultrasound images before and after the administration of contrast microbubbles to evaluate the benefit of contrast agents. Lumason, a FDA approved ultrasound contrast agent for liver imaging, will be used (IV injection) for this study. The subject will be instructed to briefly hold his/her breath during each ultrasound acquisition. Sometimes it can be difficult to find the same bowel lesion for imaging for longitudinal studies. We will measure the distance of the lesion from the ileocecal valve and use this information to help locating the same lesion for longitudinal studies.

Safety of Lumason Administration: Lumason is approved by FDA as an ultrasound contrast agent for routine clinical use. In this study, the dosage and route of administration of Lumason will comply with the guideline of the package insert of Lumason. Our study team member will screen participants to exclude pregnant women, nursing mothers, patients with known or suspected right-to-left, bi-directional, or transient right-to-left cardiac shunts, patients with history of hypersensitivity allergic reactions to ultrasound contrast agents. If a female patient with childbearing potential is not sure of her pregnancy status, a urine pregnancy test will be done. Potential side effects will be monitored by sonographer and/or radiologists: Radiology has protocols on how to respond to adverse reaction of Lumason and Definity ultrasound contrast agents

Resources: *Describe the available resources to conduct the research (personnel, time, facilities, mentor commitment, etc.):*

We have commitments from all participating personnel. Patients will be referred and recruited by participating physicians. We have a GE Logiq E9 and a Verasonics ultrasound scanner that can be used for this study.

Check all that apply. If none apply, leave blank:

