Disease activity measurements will be obtained via MR enterography at baseline and 6-months following treatment, and via ultrasound at baseline, 4-weeks and 6-months after treatment. Two quantitative ultrasound parameters will be obtained: A) shear wave speed obtained from the GE Logiq E9; B) vessel density (the percentage of pixels in the bowel lesion with blood flow compared to the total area of the lesion) obtained from the Verasonics. For each ultrasound parameter, the mean of all repeated measurements will be used as the representative value for a given patient at a given time. Measurements obtained following baseline will be expressed as percentage change from baseline. For inflammation evaluation, the correlation of each ultrasound parameter with MaRIA score will be assessed using a point estimate and 95% confidence interval. In addition, using a MaRIA cut-point of 11, patients will be categorized as having mild versus severe disease [1]. As a secondary analysis, logistic regression with corresponding ROC (Receiver Operating Characteristic) analysis will be used to assess whether ultrasound measurements can distinguish between mild versus severe inflammation. Findings from these analyses will be summarized using the point-estimate and 95% confidence interval for the area under the ROC curve (AUROC). In addition to univariate analyses, exploratory multivariable analyses will be performed to assess whether combination of ultrasound parameters can increase the performance relative to the univariate findings. Similar analyses will be performed to assess whether ultrasound parameters are useful for fibrosis evaluation: for these analyses, the MR enterography percentage gain change (PGC) will be used for correlation analysis, and a PGC cut point of 23.5% will be used to categorize fibrosis as mild or severe for ROC analysis [2].

For Aim 2, a series of analyses will be performed to assess whether ultrasound parameters obtained at baseline and 4-weeks can predict 6-month treatment outcome. A correlation analysis will be performed to assess the association of the percentage change in ultrasound parameters from baseline to 4-weeks with the percentage change in MaRIA score from baseline to 6-months. In addition, treatment outcome will be dichotomized (responder, non-responder) based on the 6-month MR enterography. Univariable and multivariable logistic

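### The measured lesion is chosen for its B-mode thickening, but wall thickness is never analysed, so the planned analyses cannot show what stiffness or vessel density adds to it

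*Combined protocol and SAP*

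**What the plan says.** All references are to the combined protocol and SAP.

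- **Purpose, Aims.** The overall goal is to "investigate the value of ultrasound measurements of small bowel stiffness and vascularity as new biomarkers for Crohn's disease". Aim 1 concerns correlation with MR enterography, and Aim 2 prediction of treatment response. No comparator among ultrasound measures is named.
- **Subject Information, Inclusion criteria.** Entry is by "involvement of terminal ileum (thickness > 3mm) or other segments of small or large bowel". The thickness limit belongs to the terminal ileum route, and the imaging method behind it is not stated.
- **Study Design, Ultrasound Procedure.** "The TI lesion with the most significant thickening will be" "identified in B-mode images for subsequent measurements". Shear wave speed and vascularity are then measured at that lesion.
- **Statistical Considerations, Power Statement.** The primary test compares the ultrasound–MaRIA correlation with 0.70, two-sided at 0.05. With a true value of 0.82 and N=100, power is given as 82%.
- **Statistical Considerations, Data Analysis Plan.** "Two quantitative ultrasound parameters will be obtained": shear wave speed and vessel density. Beyond the univariate work, "exploratory multivariable analyses will be performed to assess whether combination of ultrasound parameters can increase the performance relative to the univariate findings". The Aim 2 correlation, logistic and ROC analyses use the same ultrasound parameters. Significance is declared at two-tailed p < 0.05.

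Wall thickness is not listed anywhere as a recorded variable, covariate, comparator or predictor.

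**The concern.** The operator has to judge wall thickness on B-mode before taking either new measurement. If thickness, stiffness and blood flow all follow disease severity, a correlation of shear wave speed or vessel density with MaRIA may partly or wholly be an indirect reading of thickness. The same holds for PGC, for an AUROC, and for Aim 2, where a 4-week change in a new parameter could simply accompany wall thinning.

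A marginal correlation or AUROC cannot tell these explanations apart, and the multivariable models set the two new parameters only against each other. A positive trial could thus report that both track MR enterography, yet leave open whether they say anything that the B-mode image did not already show. Adding thickness after the results are known would be a post hoc analysis.

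**Working it through.** **Inputs from the Power Statement.** Null correlation 0.70, assumed true correlation 0.82, N=100, two-sided alpha 0.05.

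**Assumed inputs.** The documents give no correlation of thickness with MaRIA, PGC, shear wave speed or vessel density. The values below are a range, not estimates. All 100 patients are taken as evaluable unless stated.

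**Step 1: the plan's own figure.** By Fisher z, power = Φ[(atanh 0.82 − atanh 0.70) × √(N−3) − 1.96].
(1.1568 − 0.8673) × √97 = 2.851, and Φ(2.851 − 1.96) = 81.4%. Simulation with 40,000 runs gives 82.3%. The stated 82% reproduces.

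**Step 2: the observed correlation needed to pass.** tanh(atanh 0.70 + 1.96/√97) = 0.788, about 0.79.

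**Step 3: a parameter with nothing beyond thickness.** Its partial correlation with MaRIA given thickness is zero, so its marginal correlation is the product r(parameter, thickness) × r(thickness, MaRIA). Probability of passing = Φ[(atanh r − atanh 0.70) × √97 − 1.96].

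| Both components | Product r | (atanh r − atanh 0.70) × √97 | Passes the 0.70 test |
|---|---|---|---|
| 0.80 | 0.640 | −1.075 | about 0.1% |
| 0.85 | 0.7225 | 0.449 | about 7% |
| 0.90 | 0.810 | 2.558 | about 72.5% |

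To reach the plan's 0.82 with no added information, each component must be √0.82 = 0.906. To reach 0.70, each must be √0.70 = 0.837.

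**Step 4: correlations judged only at p < 0.05.** The null is now zero, so power = Φ[atanh r × √97 − 1.96].

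- Components 0.50 and 0.50: r = 0.25, and Φ(2.516 − 1.96) = 71%.
- Components 0.60 and 0.60: r = 0.36, and Φ(3.712 − 1.96) = 96%.

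**Step 5: can N=100 support an added-value analysis?** The partial correlation given thickness has Fisher z standard error 1/√(N−4). The value detectable with 80% power is tanh[(1.96 + 0.8416)/√96] = 0.28. With 85 evaluable patients it is 0.30, and with 70 it is 0.33.

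If the parameter–MaRIA correlation is 0.82 as planned, the partial correlation is (0.82 − r_PT × r_TM)/√[(1 − r_PT²)(1 − r_TM²)], where r_PT is parameter–thickness and r_TM is thickness–MaRIA.

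| r_TM | r_PT | Partial correlation | Power, N=100 |
|---|---|---|---|
| 0.70 | 0.70 | 0.65 | >99% |
| 0.80 | 0.80 | 0.50 | >99% |
| 0.80 | 0.90 | 0.38 | about 98% |
| 0.85 | 0.90 | 0.24 | 67% |
| 0.90 | 0.90 | 0.05 | 7% |

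Over r_TM from 0.5 to 0.8 and r_PT from 0.4 to 0.9, power is at least 97%. The analysis fits the planned sample size unless the new parameter is close to a restatement of thickness.

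**The case against.** The strongest reply is that the protocol asks a different question. Ultrasound is put forward as an alternative to CT and MRI for follow-up, utility is defined as a correlation with MaRIA of at least 0.70, and nothing claims superiority to thickness. The one gain the background expects, from combining elasticity and vascularity, has its own planned analysis. This stands in part: the plan does not contradict itself, and its primary test answers the question it sets. It does not remove the gap, because the stated goal is the value of new biomarkers and the lesion is itself chosen on thickening.

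A second reply is that the 0.70 threshold already screens out moderate proxies. That is right for the primary test (Step 3). It does not protect the secondary and Aim 2 correlations (Step 4).

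A third is that vessel density is a percentage of lesion area, so it need not rise with thickness by construction. True, but lesion area may itself depend on wall thickness, so the percentage is not independent of it by construction either.

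A reader might also infer more than the documents support:

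- *That all patients are selected on thickening.* Involvement of other bowel segments also qualifies, with no thickness limit. Only the choice of lesion clearly rests on B-mode thickening.
- *That the new measurements are being sold against an established B-mode follow-up.* The only clinical standards named are CT and MRI.
- *That vessel density requires contrast.* Images are taken before and after contrast to evaluate its benefit. The second scanner is stated; a need for contrast is not.
- *That the trial could never answer the question.* The limit lies in the planned analyses. B-mode imaging is already part of the procedure.

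**Conclusion.** The concern holds as a gap in the analysis plan, and one that is cheap to close. As written, no analysis separates the information in shear wave speed or vessel density from the thickening seen on the same scan, for MaRIA, PGC or treatment response.

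The exposure is uneven. The primary test is seriously exposed only if both unknown correlations are near 0.90. The correlations judged at p < 0.05 are exposed at much weaker values, from about 0.50 each. These figures rest on assumed correlations, Fisher z and 100 evaluable patients. No size is put on the AUROC analyses.

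A reader might go further and conclude that the new-biomarker claim should rest on the added-value results instead of the 0.70 test. The documents do not support that: the Power Statement makes 0.70 the criterion of clinical utility and sizes the trial for it.

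**What to change.** In the Data Analysis Plan, add B-mode wall thickness of the measured lesion as a recorded variable at baseline, 4 weeks and 6 months, taken from the B-mode imaging already performed. Then pre-specify as a secondary analysis:

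1. The correlation of thickness with MaRIA and PGC, and the partial correlation of each new parameter with MaRIA and PGC given thickness, with 95% confidence intervals.
2. In the logistic and ROC analyses for Aims 1 and 2, thickness alone against thickness plus the new parameter or parameters, by likelihood ratio test and with AUROC and 95% confidence interval for each model. In Aim 2, enter thickness as its percentage change from baseline to 4 weeks, like the other parameters.

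Keep the 0.70 primary test and its conclusion unchanged. Limit any statement of value beyond thickness to these secondary results.

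The cost is one thickness reading per scan and one more model term, with no added visit or scan. The documents do not say whether B-mode images are stored; if they are not, the reading must be made at the scan. The other cost is that the resulting claim may be less favourable.

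### The percentage-change rule has no Aim 1 exception, so the 6-month Aim 1 correlation would be computed on a scale that does not match the 0.70 benchmark; Aim 2 would gain from a supplementary baseline-adjusted analysis

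*Combined protocol and SAP*

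**What the plan says.** All references are to the combined protocol and SAP.

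- **Data Analysis Plan, general rule:** "Measurements obtained following baseline will be expressed as percentage change from baseline". No aim is named and no exception is given. The two sentences before it concern the ultrasound parameters and the averaging of their repeated measurements. The Aim 1 analyses follow it directly.
- **Study Design:** for Aim 1, "correlation of ultrasound measurements with MR enterography results will be evaluated at baseline and 6-months".
- **Power Statement:** "the correlation between ultrasound measurements and MaRIA score will be compared to 0.70". No time point is given for this test.
- **Data Analysis Plan, cut-points:** "using a MaRIA cut-point of 11, patients will be categorized as having mild versus severe disease", and "a PGC cut point of 23.5% will be used to categorize fibrosis as mild or severe for ROC analysis". Both are values of the score itself, not of its change.
- **Data Analysis Plan, Aim 2:** the planned correlation is the "association of the percentage change in ultrasound parameters from baseline to 4-weeks with the percentage change in MaRIA score from baseline to 6-months". No adjustment for either baseline is stated. The logistic and ROC analyses also take the 4-week percentage change as predictor. They name no baseline covariate and no baseline-only comparator.

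The closing clause on transformations and non-parametric methods concerns distributional assumptions. It does not exempt Aim 1 from the rule.

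**The concern.** **Aim 1.** A programmer who follows the rule as written would correlate the 6-month percentage change in ultrasound with the 6-month MaRIA score. That is a different quantity from the agreement between the two methods at that visit. A change score removes most of what is stable in a patient, whereas the MaRIA score keeps it, so the correlation falls even when ultrasound tracks MaRIA exactly as well as the plan assumes. Read against 0.70, the 6-month result could look like a failure of the method when it is a result of the scale. Any 6-month ROC analysis would carry the same mismatch, with a change as predictor of an actual-score category.

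**Aim 2.** Each percentage change contains its own baseline, and the two baselines are the markers that the plan expects to be strongly correlated. Some association between the changes can therefore arise from the baselines alone. A significant result might be taken to mean that the 4-week scan supplies early information when it does not.

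**Working it through.** **1. The plan's own figure.** Inputs from the Power Statement: null 0.70, alternative 0.82, N = 100, two-sided 0.05. Using Fisher's z,

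power = Φ((atanh 0.82 − atanh 0.70)·√97 − 1.96) = Φ((1.1568 − 0.8673)·9.849 − 1.96) = Φ(0.891) = 81.4%.

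The stated 82% is reproduced. It concerns actual values.

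**2. Assumed inputs.** The documents give no SDs and no between-visit correlations. Let *s* be stability (the correlation of a marker with itself between visits) and *c* the correlation of one marker at one visit with the other marker at the other visit. The same-visit correlation is 0.82. The simulations used lognormal values with assumed mean (SD) MaRIA 15 (6), shear wave speed 2.5 (0.6) and vessel density 20% (8).

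**3. Aim 1 at 6 months, only ultrasound converted.** On the log scale,

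r = (0.82 − c)/√(2(1 − s)).

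If c = 0.82s, this is 0.82·√((1 − s)/2):

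| s | log-scale formula | simulated percentage change |
|---|---|---|
| 0.5 | 0.41 | 0.40 |
| 0.7 | 0.32 | 0.31 |
| 0.8 | 0.26 | 0.25 |
| 0.9 | 0.18 | 0.17 |

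If instead both markers reflect one disease activity with independent visit errors (reliability 0.82 each, activity stability d = 0.6 to 0.9, so c = s = 0.82d), the formula gives 0.33 to 0.11 and the simulation 0.31 to 0.11. With actual values the simulation gives 0.81.

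**4. Aim 1 at 6 months, both converted.** On the log scale, r = (0.82 − c)/(1 − s). With c = 0.82s this is 0.82, so nothing is lost. In the shared-activity model it is 0.82(1 − d)/(1 − 0.82d) = 0.65, 0.58, 0.48 and 0.31 for d = 0.6, 0.7, 0.8 and 0.9.

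**5. Aim 2, with a 4-week scan that adds nothing to the baselines.** Let the baseline correlation be b, 4-week ultrasound depend only on baseline ultrasound, and 6-month MaRIA only on baseline MaRIA, each with stability s. On the log scale the correlation of the changes is b(1 − s)/2. At b = 0.82 and s = 0.5 this is 0.82 × 0.5/2 = 0.205; at s = 0.9 it is 0.041. Simulated share of studies of N = 100 with Spearman p < 0.05:

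| b | s = 0.5 | 0.7 | 0.8 | 0.9 |
|---|---|---|---|---|
| 0.82 | 48–50% | 21–22% | 11–13% | 7–8% |

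Over the same stabilities the share is 5–22% at b = 0.5 and 5–11% at b = 0.3. The baseline-adjusted 4-week test rejects in 4–6% throughout.

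**6. Aim 2, the opposite case.** Suppose each patient has a stable level, visit errors are independent, and every cross-marker correlation is 0.82. The four cross-marker terms cancel, so the correlation of the changes is 0 (Spearman significant in 5–6%). The partial correlation of 4-week ultrasound with 6-month MaRIA given both baselines is

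0.82(1 − s)/(1 + s − 2·0.82²).

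At s = 0.83 this is 0.1394/0.4852 = 0.29, and at s = 0.90 it is 0.082/0.5552 = 0.15. With Φ(atanh(r)·√95 − 1.96), the adjusted term is significant in about 82% and 30% of studies (simulated 83% and 31%). It acts as a second reading of an unchanged level.

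**7. Power of the adjusted test.** At partial correlation 0.3, Φ(atanh(0.3)·√95 − 1.96) = Φ(1.06) = 85% (simulated 85–87%).

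**The case against.** **The sponsor probably meant Aim 2 only.** The Aim 1 text speaks of the MaRIA score and of cut-points on it, while the Aim 2 paragraph spells out percentage change. Study Design names no scale, and the Power Statement does not say that the 0.70 test is repeated at 6 months. This is a fair account of the likely intention, and it is why the remedy is one sentence. It does not remove the problem: the rule is explicit, has no exception, and precedes the Aim 1 analyses.

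**A reader might infer that the MRE scores are converted too**, because the paragraph opens with "Disease activity measurements will be obtained via MR enterography at baseline and 6-months following treatment, and via ultrasound". The cut-points would then lose their meaning at 6 months, and the PGC cut-point, itself a percentage, might be applied to a change. The text does not support this as the main reading, since the sentences just before the rule concern ultrasound only. Even on this reading the loss runs from none to a correlation of about 0.3, depending on assumed structure.

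**A reader might infer that the Aim 2 correlation is invalid or has an inflated type I error.** It is not: it is a valid association, and the plan speaks of association and prediction, never of added value. The shares in step 5 are not error rates for that association. The 50% is also an extreme setting. It needs a baseline correlation of 0.82, which is not a natural assumption for stiffness against an inflammation score, given that the Background links stiffness to fibrosis.

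**A reader might connect this artefact to lesion relocation**, since the Ultrasound Procedure says "Sometimes it can be difficult to find the same bowel lesion for imaging for longitudinal studies". Independent visit error does not produce it (step 6 gives a correlation of 0), and the procedure uses distance from the ileocecal valve to relocate the lesion.

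**No large ROC distortion is shown.** With an illustrative response of 6-month MaRIA below 11 and no added 4-week information, the fitted univariable AUROC was 0.59–0.61, against 0.55 for pure noise.

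**Conclusion.** The Aim 1 point stands as an error in the written rule. Followed literally, it would show a same-visit correlation of 0.82 as about 0.4 to 0.1 at 6 months. The size rests on assumed stability of 0.5 to 0.9 and on ultrasound alone being converted; the direction does not depend on the exact values in that range. The baseline Aim 1 analysis and the 82% power are sound.

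The Aim 2 point stands only as an inexpensive improvement. The planned analyses may stay. By themselves they cannot show what the 4-week scan contributes beyond the baselines: the correlation can be significant without any contribution, and zero when there is one. How often this happens depends heavily on the baseline correlation and on stability, neither of which is known.

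**What to change.** **Aim 1 (should be changed).** Confine the percentage-change rule to Aim 2. State that Aim 1 at 6 months uses actual 6-month ultrasound values against actual 6-month MaRIA and PGC, with both cut-points applied to actual values. This costs one sentence and needs no new data.

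**Aim 2 (supplementary).** Keep the change-versus-change correlation and the logistic models as planned, including the models that combine stiffness and vascularity, because that combination is the study's stated rationale. Add:

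- a regression of 6-month MaRIA on baseline MaRIA, baseline ultrasound and 4-week ultrasound, transformed if needed, with a test of the 4-week term;
- a baseline-only model as comparator for the AUROC. In the illustrative no-information setting, baseline-only models reached 0.75–0.95 and the 4-week scan added 0.002–0.008, so an AUROC without this comparator is hard to interpret.

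**Cost.** All values are already collected. The regression carries two extra covariates and may give a less favourable result than the unadjusted correlation; its power at N = 100 remains about 85% for a partial correlation of 0.3. The logistic comparator is limited by the number of responders: with an illustrative 27 in 100, three terms leave 27/3 = 9 per term. A significant adjusted 4-week term should be reported as added prediction and not as early response, because it can arise from a second reading of a stable level (step 6).
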